This clinical study will be monitored by Philips Respiromics Inc. (Sponsor) in compliance with the Code of Federal Regulations (CFR) for clinical research; namely, 21 CFR Parts 50, 54, 56 and 812 and others as applicable. The purpose of such monitoring is to assure that the study remains in compliance with the approved protocol, investigator agreement and regulatory requirements, and to resolve any issues that arise during the conduct of the study. The monitoring process includes initial site qualification, periodic visits to the site, and a final visit to the site once the study is complete. Monitoring visits are scheduled periodically throughout the conduct of the study to assure compliance with the investigational plan, and to verify the completeness and accuracy of study data. Monitoring also aids in identifying any research-related problems for the sponsor and/or investigator to correct. The Sponsor will conduct monitoring visits with appropriately trained clinical research professionals.

X. Confidentiality

Confidentiality of participant identification and test-related information is very important. The privacy rules and requirements according to governing regulations will be implemented. Methods to protect the privacy of participants and clinical information will be used. A unique identification number designed to protect the identity of participants will be used to identify the participant on report forms, recruitment logs, data forms or other reports containing information or referring to a participant.

A Pilot, Multi-Center, Randomized, Open-Label, Parallel Group Study to Assess the Effects of a Novel Application of Averaged Volume Assured Pressure Support Ventilation (AVAPS-AE) therapy on Re-hospitalization in Patients with Sleep-Disordered Breathing with co-morbid COPD.

Confidential

X. References

1. Trends in Chronic bronchitis and emphysema. Morbidity and Mortality. . Part II ALA Epidemiological and Statistics unit Research and Program Services. May 2005.
2. Trends in Chronic bronchitis and emphysema. Morbidity and Mortality. Part II. ALA Epidemiological and Statistics unit. Research and Program Services. 2005 May.
3. <http://www.lung.org/lung-disease/copd/resources/facts-figures/COPD-Fact-Sheet.html#Sources>. 2013;Last accessed March 12, 2014.

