Currently, Medicare patients who are readmitted within 30-days could result in significant fines to healthcare providers and institutions. Innovations in healthcare delivery aided by device technology that expeditiously facilitates positive airway pressure therapy could mitigate such financial liabilities. Averaged Volume Assured Pressure Support –Auto EPAP (AVAPS-AE) device can not only prevent the nocturnal hypoventilation due to COPD, but also treat coexisted obstructive sleep apnea ⁽⁶⁾. AVAPS-AE is a mode of therapy (Philips Respironics Inc, Monroeville, Pa) with potential advantages over the currently established modes of noninvasive positive pressure ventilation (CPAP and bi-level therapy). This mode of therapy incorporates AVAPS (automated adjustable IPAP setting to maintain target ventilation with a settable rate of change), Auto EPAP and Auto Back up Rate. It automatically adjusts EPAP in response to patient events such as snores, leaks, and apneas / hypopneas, provides an automatic back up rate and automatically adjusts pressure support in order to maintain the target tidal volume. In a prospective cohort study, Marin and colleagues have shown that positive airway pressure (PAP) therapy treatment for “COPD-OSA overlap syndrome” can reduce a composite index of hospitalizations and mortality ⁽⁷⁾. A prospective multi-center study of PAP therapy aimed at reducing re-hospitalization due to COPD has not been performed.

A Pilot, Multi-Center, Randomized, Open-Label, Parallel Group Study to Assess the Effects of a Novel Application of Averaged Volume Assured Pressure Support Ventilation (AVAPS-AE) therapy on Re-hospitalization in Patients with Sleep-Disordered Breathing with co-morbid COPD.

Confidential

II. Study Design

This is a multicenter, randomized, parallel-group, open label study of the efficacy of AVAPS-AE to prevent re-hospitalization in hospitalized patients with comorbid COPD. A wash-in period – aimed at assessing device tolerance – will be performed in order to exclude participants who are at high risk for discontinuing positive airway pressure (PAP) therapy. Similar to pharmaceutical studies, such a wash-in period for medication tolerance can help reduce attrition and missingness that can adversely affect study sample size estimations.

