Over the first 30 days post discharge, participants in the intervention arm will receive 3 phone calls to promote PAP therapy and medication adherence. Participants in the standard of care (SOC) arm will also receive 3 phone calls to promote medication adherence over the first 30 days post discharge. On days 30 and 60, all participants will receive a phone call to determine if they had been admitted to the hospital, or had an unplanned visit to a physician’s office or emergency room. Information regarding hospital

A Pilot, Multi-Center, Randomized, Open-Label, Parallel Group Study to Assess the Effects of a Novel Application of Averaged Volume Assured Pressure Support Ventilation (AVAPS-AE) therapy on Re-hospitalization in Patients with Sleep-Disordered Breathing with co-morbid COPD.

Confidential

admission, diagnostic tests, medication changes, and procedures will be collected from all participants. Discharge summaries of re-hospitalizations and office or ER visits, as well as diagnostics tests and therapies received will be collected for measuring healthcare costs.

Participants who enrolled in a registry (optional) for a 3 year follow-up will also be queried on a yearly basis regarding hospitalizations, cardiovascular events, and assessment of vital statistics in the National Death Index registry. The study will conclude when all randomized participants have been followed for a minimum of 60 days. An independent Data Safety and Monitoring Committee (DSMC) will monitor safety data on an ongoing basis and may recommend that the study be stopped earlier in case of safety concerns. No Interim efficacy analyses is planned. Ongoing DSMB review is planned to assess device and/or safety related clinical events and adjudicate if applicable. This will be performed after 25%, 50% and 75% of target enrollment have been completed. Participants will be followed for occurrence of death or hospitalization throughout the duration of the study for a minimum of 24 months after randomization. All death and hospitalization reports will be collected on an ongoing basis during the study and will be adjudicated by an adjudication committee consisting of three site investigators.

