AVAPS-AE is a mode of therapy (Philips Resironics Inc, Monroeville, Pa) with potential advantages over the currently established modes of non-invasive positive pressure ventilation (CPAP and bilevel therapy). This mode of therapy incorporates AVAPS (automated adjustable IPAP setting to maintain target ventilation with a settable rate of change), Auto EPAP and Auto Back up Rate. We believe that these automated parameters will allow better nocturnal ventilatory control to offset the differing elastic and resistive loads imposed by changes in body position during sleep. Furthermore, AVAPS-AE will counter the changing ventilatory requirements due to alterations in lung volumes and airway resistance during different stages of sleep. In summary, the AVAPS-AE mode will enable automatic adjustment in response to ventilatory changes throughout the night. The device platform used in this study with the AVAPS-AE feature is in the BiPAP A40 platform. This device uses existing modes of therapy, therapy features, and algorithms as that which have been previously cleared by the Food and Drug Administration (FDA) (K121623).

III. Study Objectives/Endpoints

Specific aim #1: Evaluate the effects of novel application of Averaged Volume Assured Pressure Support (AVAPS-AE) therapy on time to (# of days) emergent and non-emergent healthcare utilization in patients with sleep-disordered breathing who are hospitalized with co-morbid COPD.

Specific aim #2: Evaluate the effects of novel application of Averaged Volume Assured Pressure Support (AVAPS-AE) therapy on the number of emergent and non-emergent healthcare utilization over 6 months;

A Pilot, Multi-Center, Randomized, Open-Label, Parallel Group Study to Assess the Effects of a Novel Application of Averaged Volume Assured Pressure Support Ventilation (AVAPS-AE) therapy on Re-hospitalization in Patients with Sleep-Disordered Breathing with co-morbid COPD.

Confidential

costs related to re-hospitalization; number of visits to physician offices or emergency rooms, and health-related quality of life (disease-specific and general HR-QOL measures).

Primary Endpoints

Composite end-point of time to occurrence of emergent healthcare utilization (such as re-hospitalization, unscheduled physician office visits, urgent care visits or emergency room visits).

Secondary Endpoints:

1. Healthcare Costs
2. Change in quality of life (SF-36) at 30 and 60-days
3. Change in quality of life (FOSQ) at 30 and 60-days

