- One week Device Adherence Assessment (Intervention Group)

During the first 2-7 business days post discharge, research staff will evaluate participant's device adherence via remote download. Participants with poor adherence to AVAPS-AE at home (adequate adherence defined as \geq 4 hours of use on at least 5 of the first 7 nights) will not be included in the "per-protocol analysis" (Such participants will, however, be considered in the intention to treat analysis). Per the investigators discretion, the device setting parameters may be adjusted at this time.

- Weekly Phone Follow-ups (Initial 30 days only):

Phone calls will be made weekly (\pm 2 business days) by the study coordinator to assess mask interface issues (Intervention group) and encourage adherence to AVAPS-AE (Intervention group) and medications (both intervention and SOC group). If participants require an additional visit related to issues noted above, this visit may occur either in the home or as an office to the study site.

- Day 30

At 30 days (\pm 2 business days) post discharge, participants in both Intervention and SOC groups will receive a phone call to determine if they had been admitted to this hospital, or had an unplanned visit to a physician's office or emergency room. Participants will be asked to complete FOSQ and SF-36 questionnaires. Participants will be given the option of completing the questionnaires verbally via phone call or completing handwritten copies and returned via direct mail. Postage paid return envelopes will be provided to participants who elect to complete and return the surveys by mail.

- Day 60

On day 60 (\pm 2 business days), participants in both Intervention and SOC groups will receive a phone call to determine if they had been admitted to this hospital, or had an unplanned visit to a physician's office or emergency room. Participants will be asked to complete a final FOSQ and SF-36 questionnaire. Participants will be given the option of completing the questionnaires verbally via phone call or completing handwritten copies and returned via direct mail. Postage paid return envelopes will be provided to participants who elect to complete and return the surveys by mail. Participants in both

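### Adjudication covers only one of the four listed primary components, no masking of the committee is described, and no written rule decides which visits count as emergent

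*Combined protocol and SAP*

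**What the plan says.** Section II calls the trial a "multicenter, randomized, parallel-group, open label study". On endpoint review, the same section says "All death and hospitalization reports will be collected on an ongoing basis during the study" and that these reports "will be adjudicated by an adjudication committee consisting of three site investigators". It gives no other remit for this committee. The available text does not mention redacted packets, a charter, recusal from own-site cases or masking to arm.

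Section III defines the primary endpoint as time to emergent healthcare utilization, "such as re-hospitalization, unscheduled physician office visits, urgent care visits or emergency room visits". Secondary endpoint 6 is the non-emergent counterpart. It lists scheduled admissions and scheduled office visits, and then urgent-care and ER visits again.

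Section VI describes calls at Day 30 and Day 60 to "determine if they had been admitted to this hospital, or had an unplanned visit" to an office or emergency room. The caller is not named, and neither is urgent care. Sections II and VI also collect discharge summaries and records of office and ER visits; their stated purpose is to measure costs.

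Section II gives the safety board a separate role: "Ongoing DSMB review is planned to assess device and/or safety related clinical events and adjudicate if applicable".

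**The concern.** The committee reviews the component that needs least judgement. Whether a patient was admitted is largely a matter of record. Whether an office visit was unscheduled, or whether an urgent-care or ER visit belongs to the primary endpoint or to secondary endpoint 6, has to be decided by someone. The plan does not say who decides, by what rule, or without knowledge of arm.

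If borderline visits are classified even slightly differently by arm, the primary comparison is biased, and a larger sample would not remove that bias. The same decision moves events into or out of secondary endpoint 6, so both endpoints are exposed.

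**Working it through.** **Remit against endpoint.** The table sets the committee's remit in Section II beside the endpoints in Section III.

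| Event | Primary composite | Secondary endpoint 6 | Sent to committee |
|---|---|---|---|
| Hospitalization | yes (re-hospitalization) | yes, if scheduled | yes |
| Office visit | yes, if unscheduled | yes, if scheduled | no |
| Urgent-care visit | yes | yes | no |
| ER visit | yes | yes | no |
| Death | not listed | not listed | yes |

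One of four listed primary components is adjudicated and three are not. Urgent-care and ER visits appear by name in both endpoints, so the type of visit alone does not settle where it counts. The safety board's role does not fill the gap, because it concerns device and safety events.

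**Overlap between adjudicators and patients.** Section V caps a site at 25% of total N and allows up to 10 sites.
- If the three members come from three different sites (an assumption), those sites could supply up to 3 × 25% = 75% of participants, or 60 of 80.
- With ten equal sites the share is 3/10 = 30%, or 24 of 80.

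Investigators may have device settings adjusted at the one-week check (Section VI), so a member may know the arm of patients at his or her own site.

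**The plan's own figure.** Section V enrolls 80 to obtain 60 completers at 25% attrition: 60/(1 − 0.25) = 80, which reproduces. No alpha, power or effect size is stated, and this point needs none.

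**Illustration of sensitivity.** Assume no true effect, proportional hazards, a true event risk *p* in both arms, and an extra share *d* of standard-of-care (SOC) patients counted as having an event. The apparent hazard ratio (AVAPS-AE versus SOC) is

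HR = ln(1 − p) / ln(1 − p − d)

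| Base risk *p* | *d* = 5 points | *d* = 10 points |
|---|---|---|
| 20.5% | ln 0.795 / ln 0.745 = 0.78 | ln 0.795 / ln 0.695 = 0.63 |
| 35% | ln 0.65 / ln 0.60 = 0.84 | ln 0.65 / ln 0.55 = 0.72 |
| 60% | ln 0.40 / ln 0.35 = 0.87 | ln 0.40 / ln 0.30 = 0.76 |

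The 20.5% is the protocol's expected 30-day readmission rate (Risks and Discomforts), borrowed here as a base risk for the composite. At a constant hazard it implies 1 − 0.795² = 36.8% by Day 60 for re-hospitalization alone, which is close to the middle row. The 35% and 60% rows and both shifts are assumptions.

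With 40 per arm (80 split equally, also an assumption), 5 points is 2 patients and 10 points is 4.

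The direction is not fixed. Section VI allows extra visits prompted by the weekly calls, in which mask problems arise only in the intervention arm, and does not say whether such visits count as unscheduled. If the extra events fell in the intervention arm instead, the 35% row would become ln 0.60 / ln 0.65 = 1.19 and ln 0.55 / ln 0.65 = 1.39.

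**The case against.** The case against has several parts, and some of it stands.

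- **Masking.** A reader might infer that the committee is unblinded. The documents do not say so. Open-label treatment with masked endpoint review is a normal combination, so the design alone does not show what adjudicators see. What can be said is that no masking is described.
- **Who takes the report.** A reader might infer that visits are reported to a coordinator who knows the arm. Section VI names the coordinator for the weekly calls in the first 30 days, but not for the Day 30 and Day 60 calls that collect utilization.
- **Other evidence.** The phone report is not the only source, since discharge summaries and office and ER records are collected. However, no section uses them to confirm that a visit was emergent or unscheduled.
- **How much judgement is involved.** In the primary endpoint, the word unscheduled is attached only to office visits, and the fact of an ER visit or admission is hard to dispute. That limits the room for bias. It does not remove it, because secondary endpoint 6 claims urgent-care and ER visits too. That overlap is a fault in the definition, which masking alone would not cure.
- **Effect of one misclassified visit.** In a time-to-first-event analysis, it adds an event only if the patient has no other qualifying event; otherwise it can only move the date. Section VII also plans a count approach to repeated events, and there each misclassified visit adds to the count.
- **Pilot status.** With up to 80 participants, how much adjudication to add is partly a matter of preference. Section II nevertheless describes a study of efficacy, and a biased pilot estimate would carry forward into any later trial.

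**Conclusion.** The concern holds as a gap in scope and definition. The remit covers one of four listed primary components, urgent-care and ER visits are named in both the emergent and the non-emergent endpoint, and neither a rule nor a masked reviewer is described for deciding between them. These statements rest on the text and need no assumption beyond the pages available for review.

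The size of any bias cannot be derived from the documents. The hazard ratios, 0.63 to 0.87 across the base risks and shifts shown, indicate how sensitive a trial of this size is to a handful of classifications. They should not be read as an estimate of the bias to expect, and they assume that all the misclassification falls in one arm. They also say nothing about the committee's present work, since its remit excludes these visits.

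This should be changed because the remedy is cheap and bears on the primary comparison.

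**What to change.** Keep the three-person committee and change four things before any classification is made.

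1. **Definition.** Write one definition of emergent or unscheduled use that places every hospitalization and every office, urgent-care and ER visit in either the primary endpoint or secondary endpoint 6, never both. State how visits prompted by the weekly study calls are treated.
2. **Remit.** Have the committee classify every reported hospitalization and every such visit against that definition.
3. **Masking.** Supply packets with arm, device and adherence information removed. Where possible, the two members from other sites review first, and the third sees the masked packet only to break a tie. Plain recusal would leave two reviewers and no tie-break, for up to 75% of participants on the assumption above.
4. **Records.** Use the discharge summaries and office and ER records already collected for costs. Add urgent-care records, which are not on that list.

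The cost is charter wording, coordinator time for redaction, collection of one more type of record, and more short reviews. No new staff and no change in sample size are needed. Masked classification does not recover visits that were never reported, and it does not correct care-seeking that differs by arm. Those limits of an open-label design should be stated in the report.

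### Aim 2 counts healthcare use over 6 months, but scheduled utilization contact and analysis stop at day 60; the follow-up minimums and the call questions also need reconciling

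*Combined protocol and SAP*

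**What the plan says.** In III. Study Objectives/Endpoints, Specific aim #2 evaluates the effect of the device "on the number of emergent and non-emergent healthcare utilization over 6 months". No other part of the document uses a 6-month horizon.

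**Scheduled contact.** II. Study Design states: "On days 30 and 60, all participants will receive a phone call to determine if they had been admitted to the hospital". The sentence goes on to ask about unplanned office or emergency room visits. The Day 30 and Day 60 entries in VI. Study Procedures repeat these calls, but their admission question refers to one particular hospital. In the Study Process Flow table the last utilization assessment is the 60-day call. The column after day 60 marks questionnaires, the transition plan and the optional registry only. VII. Statistical Analysis specifies results at 30 and 60 days.

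**Other sources.** Study Design adds: "Discharge summaries of re-hospitalizations and office or ER visits, as well as diagnostics tests and therapies received will be collected". This is for costing and has no end date. It also says: "All death and hospitalization reports will be collected on an ongoing basis during the study", again without contact dates. Participants who join the optional registry "will also be queried on a yearly basis regarding hospitalizations, cardiovascular events, and assessment of vital statistics".

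**Duration.** Study Design says: "The study will conclude when all randomized participants have been followed for a minimum of 60 days". In the same section, death or hospitalization is followed "throughout the duration of the study for a minimum of 24 months after randomization".

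**Endpoints.** The primary endpoint is a "Composite end-point of time to occurrence of emergent healthcare utilization (such as re-hospitalization", with unscheduled office, urgent care and emergency room visits as further examples. Secondary endpoint 5 is time to re-hospitalization, with no horizon given. Secondary endpoint 6 covers non-emergent use, including scheduled admissions and visits.

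**The concern.** An aim needs data collected to its stated horizon and an analysis at that horizon. The 6-month count has no analysis at 6 months, and part of it has no scheduled data source after day 60. Following the plan exactly would not deliver it.

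The two follow-up minimums matter because hospitalization is the one utilization event whose follow-up text runs past day 60 for all participants. In an open-label trial, the time at which events stop counting should be fixed before the data are seen.

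The call questions raise a separate issue. If they are narrower than the endpoints, events inside the 60 days are missed as well, and shortening aim 2 would not recover them.

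**Working it through.** **Inputs.** Aim 2 horizon: 6 months, taken as 180 days (Section III). Last scheduled utilization call: day 60, with a window of 2 business days either side (Sections II and VI). Minimum follow-up: 60 days, and 24 months or about 730 days (Section II). Enrolment: up to 80, with a goal of 60 completers and 25% attrition (Section V).

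**1. The plan's own arithmetic.** 60 / (1 − 0.25) = 80, which reproduces the stated enrolment. It is not in dispute and is used below only to cost the 6-month option.

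**2. Coverage of the aim 2 window.** 60 / 180 = 0.333, so 120 / 180 = 0.667 of the window follows the last scheduled call. If the call window is assumed to span up to 4 calendar days, coverage runs from 56 / 180 = 0.311 to 64 / 180 = 0.356.

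**3. The two minimums.** 730 − 60 = 670 days, about 22 months; 730 / 60 is about 12. If the study closes 60 days after the last randomisation, the last participant falls 670 days short of 24 months (ignoring the days between randomisation and discharge). Both statements cannot hold for that participant.

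**4. Events against capture routes.**

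| Event | Needed for | Day 30 and 60 calls | After day 60 |
|---|---|---|---|
| Unplanned admission | Primary composite, secondary endpoint 5, aims 1 and 2 | Asked; in Section VI, at one hospital only | Ongoing reports, undated; optional yearly registry |
| Scheduled admission | Aims 1 and 2, secondary endpoint 6 | Asked, with the same hospital limit; the question is not confined to emergencies | As above |
| Unplanned office or ER visit | Primary composite, aims 1 and 2 | Asked | No scheduled contact; undated record collection |
| Unplanned urgent care visit | Primary composite, aims 1 and 2 | Not named | No scheduled contact |
| Scheduled office, urgent care or ER visit | Aims 1 and 2, secondary endpoint 6 | Not asked, read literally | No scheduled contact; undated office and ER records |

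**5. Which horizon governs the randomised comparison.** Section II gives the intervention for 60 days, Section VI heads the post-discharge period as 60 days, and Section VII analyses 30 and 60 days. All three point to day 60. None states a censoring rule, and none says what happens to hospitalizations reported between day 60 and 24 months.

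**The case against.** The best defence is that the plan collects more than the calls alone. Study Design follows participants in general, not only registry volunteers, for death or hospitalization to 24 months, with ongoing reports and adjudication. Unless the 60-day closure rule prevails, the hospitalization part of the 6-month count has a route, though an undated one. That stands. A reader might infer that nothing is captured after day 60, and the documents do not support that.

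A reader might also infer that the primary endpoint has no usable horizon. This too goes too far. Its office, urgent care and emergency room components have no scheduled contact after day 60, and the three places in step 5 agree on day 60, so a 24-month composite is a strained reading. The censoring gap is mainly a matter for secondary endpoint 5.

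Third, the calls are not silent on non-emergent use. The admission question has no emergency restriction, so scheduled admissions fall within it. Records of office and emergency room visits are also collected without limiting them to unplanned ones. What remains is that no call clearly asks about scheduled outpatient visits, so nothing scheduled identifies which records to request.

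Finally, it is tempting to state what share of events would be lost. The documents give no utilization rate beyond 30 days and no enrolment duration, so any such share would rest on outside assumptions. None is offered here.

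**Conclusion.** The point holds as two textual mismatches and one narrower data-capture gap.

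- The 6-month horizon in aim 2 is unsupported: scheduled contact covers about a third of it, and no 6-month analysis is specified. The shortfall is clearest for office, urgent care and emergency room visits.
- The 60-day and 24-month minimums, about 670 days apart, cannot both hold for the last participants randomised. The effect is mainly an unstated censoring time for time to re-hospitalization.
- The Day 30 and Day 60 wording, taken literally, misses admissions to other hospitals, which belong to the primary composite. It also misses scheduled outpatient visits, which belong to aims 1 and 2 and secondary endpoint 6.

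The figures assume 180 days for 6 months and 730 for 24 months. The third finding depends on sites using the protocol wording as their script. A 60-day analysis of the primary endpoint remains feasible, so this should be fixed but does not undermine the design.

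**What to change.** 1. Restate the aim 2 count as over 60 days post discharge.
2. Keep the planned 30-day analysis, and name day 60 as the final censoring time for the randomised utilization comparisons. Leave the optional 3-year registry count (secondary endpoint 4) as a separate descriptive endpoint.
3. Reconcile the 60-day and 24-month statements in Study Design. Say that hospitalizations after day 60 do not enter the randomised time-to-event comparison, and give the record collection an end date.
4. Reword the two existing calls to ask about admission to any hospital, and about both scheduled and unplanned office, urgent care and emergency room visits.

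This costs protocol wording and slightly longer call scripts, with no new visits or participants. The price is a narrower aim.

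The choice of horizon is the sponsor's. If 6 months is kept, the plan needs one added contact for all participants with the same questions and a prespecified 180-day analysis. That means 60 to 80 extra contacts, each with a record request. It should also acknowledge that, under the Transition Plan, device access and use may change in both arms after day 60, so a 180-day comparison would no longer reflect the randomised 60-day contrast alone.
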